- In addition, any subject who experiences an AE of pelvic / lower abdominal pain in this study will be evaluated for possible hypersensitivity / allergic reaction including central laboratory evaluation and case adjudication (see below for further details on hypersensitivity / allergy).

Per the definition by the American College of Obstetricians and Gynecologists, chronic pelvic pain is pain in the pelvic area that lasts for 6 months or longer. In those subjects reporting lower abdominal / pelvic pain at any time during the study, either spontaneously or in response to the regularly scheduled PRO tool and who have been judged to have experienced an AE, it will be determined if duration of the pain meets this definition. The percentage of subjects in each group (laparoscopic and hysteroscopic) who are determined to have new onset or worsening chronic pelvic / lower abdominal pain will be reported. Additional analyses will be carried out looking at total number of pain reports (regardless of chronicity), intensity, and pain interference.

- **Bleeding:** The proportion of subjects reporting AEs of abnormal uterine bleeding (AUB) after insertion of Essure System compared to the proportion of subjects reporting AEs of AUB after laparoscopic tubal sterilization. Total incidence of new onset or worsening abnormal bleeding events will be based on AE reporting. If a potential bleeding AE is reported at a scheduled visit or if the subject spontaneously reports such an event to the site at some other time, the event will be evaluated per standard AE assessment. In the event of a report outside of a scheduled visit or scheduled PRO administration, the Aberdeen Menorrhagia Severity Scale (AMSS) and two intermenstrual bleeding questions will not be re-administered as the recall period for these PRO tools is 3 months and these data are captured during the scheduled PRO tool administration which occurs every 3 months.

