9.6 Safety

9.6.1 Adverse events

9.6.1.1 Definitions

Section modified by Amendment 1 (Section 16.1) and Amendment 2 ([Modification 4](#), [Modification 20](#), [Modification 21](#), [Modification 22](#), [Modification 23](#)).

Definition of AE

In a clinical study, an AE is any untoward medical occurrence (i.e., any unfavorable and unintended sign [including abnormal laboratory findings], symptom, or disease) in a clinical investigation subject after providing written informed consent for participation in the study. Therefore, an AE may or may not be temporally or causally associated with the use of a medicinal (investigational) device.

A surgical procedure that was planned prior to the start of the study by any physician treating the subject should not be recorded as an AE (however, the condition for which the surgery is required may be an AE).

Adverse device effect (ADE)

An AE related to the use of Essure or medical devices used during laparoscopic sterilization, including AEs resulting from insufficient or inadequate instructions for use, deployment, insert placement, installation or operation or any malfunction of the investigational medical device, use error, or from intentional misuse of the medical device.

In the following differentiation between medical history and AEs, the term “condition” may include abnormal physical examination findings, symptoms, diseases, laboratory, ECG, etc.

- Conditions that started before signing of informed consent and for which no symptoms or treatment are present until signing of informed consent are recorded as medical history (e.g., seasonal allergy without acute complaints).
- Conditions that started before signing of informed consent and for which symptoms or treatment are present after signing of informed consent, at *unchanged intensity*, are recorded as medical history (e.g., allergic pollinosis).
- Conditions that started or deteriorated after signing of informed consent will be documented as adverse events. This includes intercurrent illnesses.

Definition of serious adverse event (SAE)

An SAE is classified as any untoward medical occurrence that, at any dose, meets any of the following criteria (a – g):

- a. Results in death;
- b. Is life-threatening;

The term ‘life-threatening’ in the definition refers to an event in which the subject was at risk of death at the time of the event, it does not refer to an event which hypothetically might have caused death if it were more severe.

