- Potential new or worsening allergy / hypersensitivity symptoms (e.g., itch [pruritus], rash, hives [urticarial], facial edema, angioedema, allergy to metals, flushing, anaphylaxis), in addition to symptoms that could possibly be related to an inflammatory reaction (e.g., hair loss, fatigue, muscle pain, joint pain, joint swelling);
- Potential new or worsening autoimmune reactions;
- Intraoperative bleeding or complications after undergoing hysteroscopic sterilization with Essure or laparoscopic tubal sterilization, including additional surgical procedures to manage the complications;
- Chronic pelvic pain. Per the definition by the American College of Obstetricians and Gynecologists, chronic pelvic pain is pain in the pelvic area that lasts for 6 months or

longer. In those subjects reporting new or worsening lower abdominal / pelvic pain at any time during the study, either spontaneously or in response to the regularly scheduled PRO tool, evaluation of the event will note if duration of the pain meets this definition.

- Pregnancy (refer to Section 9.6.2);
- Upper genital tract infection (for example, endometritis, salpingo-oophoritis, salpingitis).

Allergic / hypersensitivity reactions

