#### **4.4.5 Main outcome events**

Incomplete start dates of outcome events for the time to event analyses will be imputed as follows:

- In case that only the day is missing, the date will be imputed as the first day of the month.
- In case that the day and the month are missing (i.e. only the year is available) the day and month will be imputed as January 1.
- In case the event start date is missing completely, index event date will be used as start date.
- If the imputed start date is before the index date, it will set to the index date.

Incomplete stop dates of outcome events for the time to event analyses will be imputed as follows:

- In case that only the day is missing, it will be imputed with last day of the month;
- In case that the day and the month are missing (i.e., only the year is available) it will be imputed as December 31.
- If the imputed dates are after the last date of contact, it will be set to the last date of contact.
- If the stop dates are completely missing, the event will be considered as ongoing at the time of end of study.

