**Table 2 - Outcome endpoints and variables collected during treatment**

	Endpoint/Variable
Main Endpoints	
 
Subjects reporting AEs of chronic lower abdominal and/or pelvic pain after sterilization procedure
 
Subjects reporting AEs of abnormal uterine bleeding after sterilization procedure
 
Subjects with reported allergic/hypersensitive reactions
 
Subjects with newly diagnosed autoimmune disorders
 

	Endpoint/Variable
	
 
Subjects undergoing invasive gynecologic surgery (e.g., device removal or hysterectomy) after sterilization procedure (excluding second Essure placement attempts)
 

Patient Reported Outcomes	
 
MOS SF-36 (Version 2) which includes eight distinct health domains (physical function, role-physical, bodily pain, mental health, role-emotional, social functioning, vitality, and general health perceptions) and physical component summary and mental component summary scores
 
PROMIS Scale V1.0—Pain Intensity 3a, raw score, T-Scores, percentages of subjects who had T-Scores more than 50 and 60
 
PROMIS Scale V1.0—Pain Interference 8a, raw score, T-Scores, percentages of subjects who had T-Scores more than 50 and 60
 
AMSS and two intermenstrual bleeding questions used to characterize bleeding in subjects undergoing Essure placement and laparoscopic tubal sterilization, total raw scores and individual score for each question, percentage of subject having total scores greater than 40
 
FSQ: to investigate if scores on this instrument (continuous and categorical) correlate with chronic pelvic pain over the course of the study
 
Supplemental PRO Questionnaires
 
Social Media Questionnaire
 

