Adverse Events	Any AE, Serious AEs, reason for serious AE, AE of special safety interest, AE intensity, AE related to study procedures or devices, type of procedure/device related to AE, AE outcome, pre-existing condition, concomitant medication, other non-study procedures
Contraceptive Method Post-procedure	Method used for contraception, duration of the contraceptive method used.
Concomitant Medication	Type of medication, main indication for medication
Additional Abdominal or Pelvic Surgery	Type of surgery performed, was surgery done for the purpose of sterilization/ re-sterilization , surgery due to an AE
Allergy/Hypersensitivity Evaluation, Autoimmune Disorder Evaluation, and PRO Alert Response	Symptom subjects reported, adjudication committee form, pathological findings, serum or plasma nickel and titanium levels, NiLPT and chromium LPT results, cytokine samples analysis , type of alert, pain alert response and bleeding response.
Study Completion	Did subject complete study, primary reason for premature discontinuation, time to premature discontinuation
Death	Number subjects died

a Only measured for Essure Group

b Only measured for laparoscopic tubal sterilization group

For the main outcomes, [Table 3](#) lists the SMQ search terms for abnormal uterine bleeding and lower abdominal and/or pelvic pain. Per the definition by the American College of Obstetricians and Gynecologists, chronic pelvic pain is pain in the pelvic area that lasts for 6 months or longer (i.e., the stop date of the pain minus start date is longer than 182 days, or by the time of EOS, the subject still has pain ongoing with start date 182 days before EOS).

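### SAP 6.4 defines chronic pelvic pain by dates alone and does not link pain records, so a continuous pain of 183 to about 364 days split into two short AEs can be missed from the first main endpoint

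*SAP*

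**What the plan says.** **Protocol.** Section 5.2.1 adopts a 6-month definition of chronic pelvic pain. For women judged to have a pain AE, "it will be determined if duration of the pain meets this definition". The reported result is the percentage in each group "who are determined to have new onset or worsening chronic pelvic / lower abdominal pain will be reported". Section 9.6.1.1, under AEs of special safety interest, adds that the "evaluation of the event will note if duration of the pain meets this definition". Neither section names the assessor.

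**SAP.** Table 2 lists first among the main endpoints: "Subjects reporting AEs of chronic lower abdominal and/or pelvic pain after sterilization procedure". The text of Section 6.4 that follows the table repeats the 6-month definition and makes it operational in two limbs. The first is that "the stop date of the pain minus start date is longer than 182 days". The second is that "by the time of EOS, the subject still has pain ongoing with start date 182 days before EOS". Section 4.4.5 supplies the dates where they are incomplete, for example: "If the stop dates are completely missing, the event will be considered as ongoing at the time of end of study".

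The SAP does not mention the determination in Protocol 5.2.1 or the event-level note in 9.6.1.1. It does not say which source prevails if they disagree with the dates. It has no rule for joining pain AEs that follow one another, whether under the same Table 3 term or different ones.

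**The concern.** The endpoint counts women, and the clinical idea behind it is the duration of a woman's pain. The only start and stop dates for which the SAP has rules belong to AEs or outcome events (4.4.2, 4.4.5). If one continuous pain is entered as two consecutive AEs, each record is shorter than the pain. Applied record by record, the date rule can then call the woman not chronic although her pain met the 6-month definition that the protocol asks to be checked.

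At stake is the case definition of the first main endpoint, one of the few outcomes that SAP 6.4 compares between groups. Matching on baseline variables cannot repair an error in how the outcome is derived. If the question stays open, it will be settled at programming, in an open-label study.

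**Working it through.** **1. The SAP's own figure.** Half a year is 365/2 = 182.5 days, or 365.25/2 = 182.6 days. The SAP's 182 agrees. Since the duration must be longer than 182 days, a record qualifies from 183 days. (Six calendar months span 181 to 184 days depending on the starting month. That boundary is a separate, smaller matter.)

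**2. When a split pain is missed.** Take one continuous pain of T days, entered as two AEs, the second starting on the day the first stops. Let the first last m days, with m from 1 to T − 1. The pain is missed only if neither record qualifies:

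m ≤ 182 and T − m ≤ 182, that is, T − 182 ≤ m ≤ 182.

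For T of 183 or more, that is 365 − T of the T − 1 possible whole-day splits:

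share missed = (365 − T)/(T − 1).

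| T (days) | Splits missed | Share |
|---|---|---|
| 183 | 182 of 182 | 100% |
| 200 | 165 of 199 | 83% |
| 240 | 125 of 239 | 52% |
| 270 | 95 of 269 | 35% |
| 300 | 65 of 299 | 22% |
| 330 | 35 of 329 | 11% |
| 360 | 5 of 359 | 1.4% |
| 364 | 1 of 363 | 0.3% |
| 365 or more | 0 | 0% |

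Two records of at most 182 days cover at most 2 × 182 = 364 days, so one split cannot hide a longer pain. If the second record starts the next day, the limit is 365 days.

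**3. Average.** With T uniform on 183 to 365 days and every split point equally likely, the mean share is 0.387 (0.392 with a next-day restart). The continuous form agrees: the mean of (364 − D)/D for D from 182 to 364 is 2 ln 2 − 1 = 0.386. So about 39% of single splits are missed. The uniform duration and the uniform split point are assumptions.

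**4. Does the end-of-study limb help?** Only if the last record is ongoing and began early enough before end of study. A first record with a wholly missing stop date is treated as ongoing and may qualify by itself. A properly closed first record followed by a second short one is not rescued.

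**5. Can splitting arise?** Set side by side:

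- *For.* Protocol 5.2.1 has each pain alert from a scheduled questionnaire judged by ordinary AE criteria, including whether a symptom is new or has worsened. Table 9–2 schedules the pain screen every 3 months from Month 3 to Month 36, after earlier weekly and monthly screens. A worsening found at a later alert could plausibly be entered as a further AE. SAP Table 3 lists many pain terms, so the second entry may carry a different one.
- *Against.* Protocol 9.2.3.1 requires assessment only where the potential AE was not recently assessed. Section 9.2.3.4 asks for investigation only where the pain has not already been evaluated.

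Splitting is thus possible and nowhere prevented, but the documents give no frequency for it.

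**The case against.** **The SAP rule may simply be the protocol's determination in working form.** The determination is itself a duration test, Protocol 10.1 leaves calculated variables to the SAP, and SAP 6.4 speaks of the pain rather than of each AE record. This stands in part. A reader might infer that the SAP overrides a clinical judgement, but the documents do not establish two conflicting rules. They show silence on how the note is used. The silence matters because the same section does say whose decision governs allergic and autoimmune events: the adjudication committee's.

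**Nothing requires a worsening pain to be entered twice.** This stands. A reader might rely on Protocol 9.6.1.1, "Conditions that started or deteriorated after signing of informed consent will be documented as adverse events", but that sentence belongs to a list separating medical history from AEs. It does not say that an open AE which worsens is closed and re-entered. Section 9.6.1.2.2 lists three intensity grades without tying a record to one grade. The limits on repeat assessment in 9.2.3.1 and 9.2.3.4 also work against duplicates.

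**The consequence is limited.** The study is exploratory, SAP 6.5.1 tabulates all pelvic and abdominal pain AEs whether chronic or not, and every AE is listed. No report of pain disappears. But those tables do not restore the chronic label, and that label defines the main endpoint.

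**Joining records has its own hazard.** Table 3 ranges from incision site pain to back pain and dysmenorrhoea. Merging any of these within a fixed gap could create chronic pain out of distinct conditions, and the effect could differ by arm because every laparoscopy subject in the full analysis set has an incision or puncture. This stands and narrows the remedy.

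**Conclusion.** The point holds as a gap in the endpoint derivation. SAP 6.4 classifies chronicity by dates alone, does not use or mention the protocol's determination, and does not link consecutive pain AEs. Applied record by record, it can miss a continuous pain of 183 to about 364 days when neither of two records exceeds 182 days. Under the uniform assumptions this affects about 39% of single splits, falling from all of them at 183 days to almost none at 12 months.

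Three stronger readings are tempting and are not supported:

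- *That any 6 to 12 month pain entered as two AEs is lost.* A 300-day pain entered as 250 + 50 days still counts, because one qualifying record is enough; 150 + 150 does not.
- *That the loss to the endpoint can be stated.* If 20% to 40% of such pains were split, 0.39 × 0.2 to 0.39 × 0.4 gives roughly 8% to 15% of 6 to 12 month pains. The split share is a guess, and the endpoint also includes longer pains that one split cannot hide.
- *That the comparison is biased in a known direction.* Protocol 5.2.1 expects outside influences to affect AE reporting unequally, but no document gives a difference between arms in record splitting.

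**What to change.** In SAP 6.4, before the final analysis is programmed:

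1. Join pain records that overlap or are contiguous and describe the same pain in the same woman. Give the joined episode the earliest start and the latest stop, then apply the 182-day rule.
2. State how the chronicity determination of Protocol 5.2.1 and 9.6.1.1 enters the endpoint. One option is to count a woman as chronic if either the joined dates or the note says so, where the note was captured.
3. List the women for whom the two sources disagree, by group.
4. Confine any longer joining gap (such as 30 days), or joining across unrelated Table 3 terms, to a sensitivity analysis.

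The cost is a few sentences and a small derivation step on dates already collected. Whether the note exists as a data field must be checked, since the documents do not show one. The chronic-pain proportion may rise, and deciding which records describe the same pain carries some risk of merging distinct pains. The listing makes both visible.

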9.6.1.6 Device removal and surgical pathology

Section modified by Amendment 1 (Section 16.1) and Amendment 2 ([Modification 5](#)).

Each time a surgical procedure is performed (Essure or laparoscopic tubal ligation), additional information will be collected about the circumstances surrounding the surgery (e.g., date of placement, reason for removal, procedure details, any energy sources used, vasoconstrictive agent used, imaging to assist with confirming the location of the insert, and the location and status of the device removed). Subjects who have had surgical intervention or their device removed will continue to be followed for the collection of safety and laboratory data.

Prior to any planned surgical removal of an Essure insert, salpingectomy, or hysterectomy, the investigator must contact the sponsor in order to arrange for handling of the pathology specimen. This is important as improper handling of specimens may preclude the performance of metallurgic analyses.

Whenever possible, and if clinically and surgically appropriate, if the decision is to remove the fallopian tube, this should be done with the Essure insert or sterilization device, if

applicable (e.g., Falope ring, Filshie clip) in situ. In the case of Essure, this can be accomplished by making a circumferential incision around the proximal tube near the cornua, then pulling the proximal most portion of the insert from the cornua (while the remainder of the insert remains in the tube that is removed), or with a cornual resection. Physician judgment as to the appropriate procedure for the subject will take precedence over obtaining a pathology specimen. If a hysterectomy is clinically and surgically appropriate, it should be performed with the tubes attached to the uterus, if possible.

In the Essure group, ideal specimens will have the Essure insert in situ as this will provide the most complete information; however, all tubes, regardless of presence of the insert, should be submitted for examination. In addition, all inserts, regardless of whether they are in situ or previously removed, should be submitted. Processing for tubes with and without inserts in situ will need to be slightly different.

In the laparoscopic sterilization group, ideal specimens will be fallopian tubes with sterilization devices in situ, if applicable (e.g., Falope ring, Filshie clip); however, all tubes should be submitted regardless of presence of a previously applied sterilization device.

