### **4.3 Handling of loss to follow-up, premature discontinuation, and censoring**

Subjects who leave the study before reaching the study completion assessment five years after start of the sterilization procedure will be included in the analysis populations, since the analyses are based on all subjects who attempt sterilization.

For subjects who attempt two sterilization methods, or have any hysterectomy (subtotal, total or radical), or have Essure complete removal using a salpingectomy, or device removal not accompanied by sterilization procedure, their data will be censored for analysis purpose on the earliest date of second sterilization method, hysterectomy surgery date, or Essure removal date, for the primary analysis.

Data will be collected for all the subjects until the end of study or early termination.

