Hysterosalpingogram a	Timing of HSG, reason, HSG indication, TVU/HSG Algorithm requirement, type of difficult placement procedure, facility where HSG performed, uterine position at the time of HSG, insert detected (by tube), implant location (by tube), reason for unsatisfactory location (by tube), tubal occlusion (by tube), HSG results satisfactory to allow the subject to rely on Essure, individual who performed HSG, individual who interpreted HSG, experience AE during HSG
Essure Device Removal a	Physician Performing Procedure, Device removal intentional, reason for unintentional removal, primary reason for device removal, additional reasons for procedure, surgical method planned/performed, type of anesthesia, procedure related events, surgery result in permanent sterilization, procedures performed at time of device removal, reason why removal procedures were chosen, types of energy sources, vasoconstrictive agent used during removal, imaging procedures performed to localize inserts prior to removal, number of devices removed, location of device (per device removed), removal status (per device removed),
Reliance Assessment a	Timing of reliance assessment visit, imaging used for assessment, whether subject compliant and reason, subject instructed to rely on Essure inserts for contraception
Birth Control Counseling	Time of birth control counseling, reason for counseling on alternate method of birth control, method of birth control discussed with subject
Laparoscopic Tubal Sterilization b	Primary method of contraception used just prior to procedure, facility, pregnancy test performed within 24 hours of the procedure, type of procedure planned/performed, surgical method planned/performed, type of anesthesia, intraoperative findings, were both the specific procedure and surgical method completed as initially planned, complications during procedure, additional procedures performed, physician's assessment of

	Endpoint/Variable
	procedural difficulty, assessment of ability to access tubes, bilateral tubal occlusion achieved
Device Event	Any device event, type of device/problem, summary of device events, device event outcome, AE related to device event, device event evaluation

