#### **6.4.1 Subject Incidence**

The subject incidence is defined as the number of subjects with at least one event divided by the number of subjects at risk. Subject incidence will be calculated for each group. The risk difference between two groups will also be calculated. Its associated 95% CI will be derived based on normal approximation.

Additionally for the main endpoints, subject incidence and risk differences will be given for the following time intervals: Day 0, Day 1-7, Day 8-30, Day 31-90, Day 91-180, Day 181-365, Day 366-730, > Day 730.

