## 6.8 Sensitivity analyses

Sensitivity analysis will be performed for the main endpoints and summary AEs. The analysis will include all the data from index date till the end of study no matter if the subject had censoring events or not during the study.

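### Pelvic pain that surgery ends within 182 days of onset is a non-event in the chronic-pain comparison, and the planned sensitivity analysis does not recover it

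*SAP*

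**What the plan says.** The first of five main endpoints in SAP Table 2 is "Subjects reporting AEs of chronic lower abdominal and/or pelvic pain after sterilization procedure". The text below that table gives two ways to qualify as chronic. For resolved pain, "the stop date of the pain minus start date is longer than 182 days". For unresolved pain, "by the time of EOS, the subject still has pain ongoing with start date 182 days before EOS". Neither limb mentions pain that ended because of surgery. The 6-month duration comes from a professional-body definition that protocol section 5.2.1 adopts.

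For women who have a second sterilization method, a hysterectomy or an Essure removal, SAP 4.3 says that in the primary analysis "their data will be censored for analysis purpose on the earliest date of second sterilization method, hysterectomy surgery date, or Essure removal date". Subject incidence in SAP 6.4.1 is "the number of subjects with at least one event divided by the number of subjects at risk". The sensitivity analysis in SAP 6.8 uses all data to the end of the study, "no matter if the subject had censoring events or not during the study".

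Data continue to accrue after surgery. Protocol 9.6.1.6 states: "Subjects who have had surgical intervention or their device removed will continue to be followed for the collection of safety and laboratory data". The removal variables in SAP Table 2 include "primary reason for device removal", recorded for the Essure group only. The additional-surgery variables, not restricted to one group, include whether surgery was due to an adverse event.

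**The concern.** Surgery can prevent this endpoint from occurring. A woman whose pain is bad enough to lead to removal or hysterectomy within six months, and whose pain then stops, has a genuine stop date and a non-chronic adverse event. Her pain is treatment-emergent and falls inside the risk window; the duration rule alone excludes it. Longer follow-up does not help, because the pain is over.

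The documents foresee this course. Protocol 9.2.2.2 collects symptom resolution after device removal, and protocol 9.6.1.6 expects some removals to be for pain. Propensity-score matching cannot correct the problem, since it balances baseline variables and surgery comes later.

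At stake is the direction of the chronic-pain comparison. If early surgical resolution is more common after Essure, the Essure risk is understated by more than the laparoscopic risk, and effective early removal makes the device look safer on this endpoint.

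**Working it through.** The documents state no sample size, power or event rate, so there is no planned figure to reproduce. The one number is the cut-off, and it fits six months: 365.25 / 2 = 182.6 days.

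**Step 1: the rule applied to cases.** Pain starts on day 30 in each.

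- Removal and resolution on day 180: 180 − 30 = 150 days, no event.
- Removal and resolution on day 212: 182 days, no event.
- Removal and resolution on day 213: 183 days, event.
- No surgery, pain ongoing at end of study: event.
- Removal on day 180, pain continuing to end of study: event if the true course is used, but no event if the record is cut at the censoring date. The SAP does not say which applies.

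**Step 2: the planned analyses.** In subject incidence, the day-180 woman stays in the denominator without an event. In the Kaplan-Meier and Cox analyses she is event-free until she is censored at surgery. Under SAP 6.8 she is event-free for longer. The duration rule is unchanged throughout.

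**Step 3: size.** Let p be the share of women whose pain would last more than 182 days without surgery, and f the share of those whose pain surgery ends at or before 182 days. Then observed risk = p × (1 − f). Both inputs are assumptions.

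| True risk, Essure / laparoscopic | f, Essure / laparoscopic | Observed risk | Risk difference (points) | Risk ratio |
|---|---|---|---|---|
| 10% / 10% | 10% / 2% | 9.0% v 9.8% | −0.8 | 0.92 |
| 10% / 10% | 20% / 5% | 8.0% v 9.5% | −1.5 | 0.84 |
| 10% / 10% | 50% / 5% | 5.0% v 9.5% | −4.5 | 0.53 |
| 10% / 10% | 20% / 20% | 8.0% v 8.0% | 0 | 1.00 |
| 15% / 10% | 10% / 2% | 13.5% v 9.8% | +3.7 (true +5.0) | 1.38 (true 1.50) |
| 15% / 10% | 20% / 5% | 12.0% v 9.5% | +2.5 (true +5.0) | 1.26 (true 1.50) |
| 15% / 10% | 50% / 5% | 7.5% v 9.5% | −2.0 (true +5.0) | 0.79 (true 1.50) |

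**Step 4: break-even.** A true excess disappears when f in the Essure arm = 1 − (1 − f in the laparoscopic arm) / true risk ratio. For a true ratio of 1.5 this is 1 − 1/1.5 = 33% with no early surgical resolution in the laparoscopic arm, or 1 − 0.95/1.5 = 37% with 5%. For a true ratio of 2.0 it is 50% or 52.5%.

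**Step 5: scale of f.** Suppose time from pain onset to surgery is exponential with median m months and surgery always ends the pain. Since 182 days is 182 / 30.4375 = 5.98 months, f = 1 − 0.5^(5.98/m). Medians of 12, 24 and 36 months give 29%, 16% and 11%.

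**The case against.** The strongest reply is that the endpoint is chronic pain, defined on purpose by an outside professional standard and fixed in protocol 5.2.1. Pain that stops sooner is not chronic, and whether it would have become so cannot be observed. This stands as a reason to keep the definition. It does not excuse silence on what happens when surgery pre-empts the six months.

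A reader might infer that this pain vanishes from the study. It does not. Protocol 5.2.1 and SAP 6.5.1 (Adverse events, items 9 to 12) report pain of any duration. SAP Table 2 reports removal reasons. Protocol 10.5 summarises removals and their resolution when linked to an adverse event. Invasive gynecologic surgery is itself a main endpoint, and this woman can count there. But SAP 6.4 reserves comparative analysis for the main endpoints, and none of them joins pain to the surgery that ended it. SAP 6.4.1 could be read as attaching risk differences more widely; even so, any-duration pain would not single out pain that led to surgery.

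A reader might also infer that only the Essure arm can be affected. Clips and rings are used in the laparoscopic arm, and hysterectomy and salpingectomy can occur in either. The asymmetry is an inference from Essure insert removal existing in one arm only.

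Finally, the study is exploratory and tests no hypothesis. That lowers the stakes, but risk differences with intervals and hazard ratios will still be reported and read as comparisons.

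**Conclusion.** The gap follows directly from the text: pain ended by surgery at or before 182 days is a non-event in the chronic-pain comparison, with or without censoring at surgery. A bias favouring Essure is plausible but conditional. It needs early surgical resolution to be proportionally more frequent in the Essure arm; with equal shares the risk ratio is unchanged.

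The documents do not support any particular size. The figures above rest on assumed risks and shares, and on p, which cannot be observed in women who have early surgery. Nor do the documents support calling this the primary endpoint (it is the first listed of five), describing the lost cases as the most severe or device-caused, or replacing the 6-month definition. They do support one prespecified supplementary comparison that closes a foreseeable gap.

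**What to change.** Keep the present definition as the main analysis, and add the following to SAP 6.4 and 6.8.

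1. A comparative analysis (risk difference with 95% CI, Kaplan-Meier, hazard ratio) in the full and adjusted full analysis sets. The event is treatment-emergent Table 3 pain that either (i) meets the existing 182-day rule, or (ii) is open at, and a recorded reason for, Essure removal, hysterectomy, salpingectomy or other therapeutic Table 4 surgery before 182 days. Exclude diagnostic laparoscopy from (ii).
2. Identify (ii) from sources common to both arms: the adverse-event treatment category for an additional surgical procedure (protocol 9.6.1.2.4), the event and surgery dates, and the field for surgery due to an adverse event. Use the Essure-only removal form as support, not as a qualifying source, so that ascertainment does not differ by design.
3. Show (i) and (ii) separately by arm.
4. Add a comparative analysis of pain of any duration.
5. State whether pain open at the censoring date keeps its true stop date.

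The cost is SAP wording, one derivation and extra tables, with no new data and no change to the protocol definition. The downside is that some added pains would have resolved anyway, and some removals may reflect the media attention that the plan itself expects; the component split makes this visible. The rule should be fixed before the final analysis, because a rule chosen after looking at the removals would carry little weight.
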